**Randomization Criteria:**

1. Continue to meet entrance criteria
2. Negative serum (Visit 1) and urine (Visit 2, pre-randomization) pregnancy test result for all female subjects of childbearing potential
3. Stable FEV1 at Visit 2, defined as FEV1 within  $\pm 15\%$  of the relative change between the Visit 1 and Visit 2 best FEV1. Relative change is defined as follows:

$$\frac{\text{FEV}_1 \text{ (Screening; Visit 1)} - \text{FEV}_1 \text{ (Visit 2)}}{\text{FEV}_1 \text{ (Screening; Visit 1)}} \times 100$$

4. No new intervening illnesses since Screening (Visit 1) and the subject's CF is still stable in the judgment of the Investigator
5. No clinically significant laboratory or ECG abnormalities that pose a significant risk to the subject, per the judgment of the Investigator

Note: A subject may be re-screened once if they fail to meet randomization criteria for any reason. If this is the case, a new consent form must be signed, and a new screening number will be used.

**NUMBER OF SUBJECTS:**

In Cohort 1, 46 subjects were randomized in a 1:1:1 ratio to 1 of the 2 treatment groups or placebo. The sample size of 39 subjects was chosen to provide 70% power for the Analysis of Variance (ANOVA) to detect a difference range of 4.5% to 6% in the change from baseline in ppFEV1 and FEV1 between each of the 2 treatment groups versus placebo, with the alpha level of 0.15 assuming a common standard deviation of 7%. The attrition rate was expected to be minimal given the 4 weeks' treatment duration.

In Cohort 2, a total of 45 subjects will be randomized in a 2:1 ratio to either SPX-101 120 mg BID or placebo BID. The sample size of 45 subjects will provide 88% to 97% power to detect a difference range of 6% to 8% in the change from baseline in ppFEV1 between the treatment group versus placebo, with the 1-sided alpha level of 0.1 assuming a common standard deviation of 7.58%.

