### **13.2 Sample Size Estimation**

The study was planned for a minimum of 39 subjects per cohort to be enrolled. In Cohort 1, 46 subjects were randomized in a 1:1:1 ratio to one of the two treatment groups or placebo. The sample size of 39 subjects was chosen to provide 70% power for the Analysis of Variance (ANOVA) to detect a difference range of 4.5% to 6% in the change from baseline in ppFEV1 and FEV1 between the 2 treatment groups versus placebo, with the alpha level of 0.15 assuming a common standard deviation of 7%. The attrition rate is expected to be minimal given the 4 weeks' treatment duration.

In Cohort 2, a total of 45 subjects will be randomized in a 2:1 ratio to SPX-101 120 mg BID or placebo. The sample size of 45 subjects will provide 88% to 97% power to detect a difference range of 6% to 8% in the change from baseline in ppFEV1 between the treatment group versus placebo, with the 1-sided alpha level of 0.1 assuming a common standard deviation of 7.58%.

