## 6.1 Sample Size Considerations

In Cohort 1, the study was planned for a minimum of 39 subjects per cohort to be enrolled. The subjects will be randomized in a 1:1:1 ratio to one of the two treatment groups or placebo. The sample size of 39 subjects provided 70% power for the Analysis of Variance (ANOVA) to detect a difference range of 4.5% to 6% in the change from baseline in ppFEV1 and FEV1 between the 2 treatment groups versus placebo, with the two-sided alpha level of 0.15 assuming a common standard deviation of 7%. The attrition rate is expected to be minimal given the 4 week treatment duration.

In Cohort 2, a total of 45 subjects will be randomized in a 2:1 ratio to SPX-101 120 mg BID or placebo. The sample size of 45 subjects will provide 88% to 97% power to detect a difference range of 6% to 8% in the change from baseline in ppFEV1 between the treatment group versus placebo, with the 1-sided alpha level of 0.1 assuming a common standard deviation of 7.58%. The estimated treatment difference and standard deviation are based on the Cohort 1 results from the 120 mg SPX-101 dose group and placebo, among subjects with baseline ppFEV1 between 50.0% and 80.0%, since this reflects the subjects enrolled in Cohort 2.

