### 12.6.1 Primary Variable

#### Primary Efficacy Analysis

The primary efficacy endpoint is the change from baseline in ppFEV1 at visit 5 (week 4). The change from baseline in ppFEV1 at each visit (Weeks 1, 2, and 4) will be summarized and compared between each treatment group and placebo. No imputation of missing data will be done for this analysis.

The comparison between each treatment group and placebo will be evaluated by using an analysis of covariance (ANCOVA) model, which will include treatment as the factor, and the stratification factor as a covariate (i.e., baseline lung function categories [ppFEV1 40.0% to 55.0% or 55.1% to 80.0% for Cohort 1] and the concomitant use of hypertonic saline for Cohort 2). Also included in the ANCOVA model for Cohort 2 is baseline ppFEV1. Descriptive statistics will include the number of observations, unadjusted mean, standard deviation, median, first quartile, third quartile, minimum and maximum, and least squares mean. Treatment differences from placebo will be presented and estimated by least squares means from the analysis model along with 95% confidence intervals and associated 2-sided p-values, which are presented for descriptive purposes.

Sponsor: SPYRYX Biosciences

Protocol no: SPX-101-CF-201

---

As described in the power and sample size calculations in Section 6.1, Cohort 1 will be evaluated for success using a two-sided 0.15 significance level. Cohort 2 will be evaluated for success using a one-sided (upper) 0.10 significance level. For Cohort 2, both the one-sided p-value and the lower bound (i.e. one-sided 90% confidence interval) will be presented.

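### Cohort 1's 70% power is that of a three-group F test; each planned dose-versus-placebo comparison has about 57% power at 4.5 points and 76% at 6

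*Protocol*

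**What the plan says.** The protocol synopsis (Number of Subjects) gives the basis for the Cohort 1 size: "The sample size of 39 subjects was chosen to provide 70% power for the Analysis of Variance (ANOVA"). The effect sought is 4.5 to 6 points, for ppFEV1 and FEV1 alike. The comparison it belongs to is described as "between each of the 2 treatment groups versus placebo, with the alpha level of 0.15 assuming a common standard deviation of 7" percent. The synopsis does not say whether alpha is one- or two-sided.

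Protocol 13.2 repeats the figure ("70% power for the Analysis of Variance (ANOVA) to detect a difference range of 4.5% to 6" percent) but refers to the two treatment groups versus placebo without the word *each*. SAP 6.1 uses the same looser form and adds the sidedness: "with the two-sided alpha level of 0.15 assuming a common standard deviation of 7" percent.

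On the analysis, SAP 12.6.1 compares each treatment group with placebo by ANCOVA, with the lung-function stratum as the Cohort 1 covariate, and says "Cohort 1 will be evaluated for success using a two-sided 0.15 significance level". Protocol 13.6.4.1 likewise plans group-versus-placebo comparisons. SAP 12.6.6 makes no multiplicity adjustment, so each comparison uses the full 0.15. The only three-group test in the Cohort 1 plan is Kruskal-Wallis, a fallback if the model assumptions fail.

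On numbers, "46 subjects were randomized in a 1:1:1 ratio to 1 of the 2 treatment groups or placebo". Protocol 7.3.2 reports 45 treated and 40 completing.

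**The concern.** A power figure describes one test against one alternative. The synopsis attaches the power of an omnibus test to each pairwise comparison, and the analysis plan then uses the pairwise comparisons. An omnibus test can have 70% power while one of its component comparisons has clearly less.

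What is at stake is how a completed cohort is read. Protocol 7.3.2 reports differences from placebo of 3.08 (SE 2.411, p = 0.21) for 60 mg BID and 5.19 (SE 2.606, p = 0.05) for 120 mg BID. Someone judging how well each dose was tested would take 70% from the synopsis, whereas the planned comparison has about 57% if the true difference is 4.5 points.

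**Working it through.** **Inputs.** Total 39 at 1:1:1, so 13 per arm; SD 7; alpha 0.15; differences 4.5 and 6 (synopsis and protocol 13.2). Two-sided (SAP 6.1 and 12.6.1). No allowance for dropout: "The attrition rate was expected to be minimal". No multiplicity adjustment (SAP 12.6.6).

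**Step 1: reproduce the stated 70%.** One-way ANOVA with group means 0, 4.5 and 6.
- Grand mean = (0 + 4.5 + 6)/3 = 3.5. Squared deviations: 12.25 + 1 + 6.25 = 19.5.
- Noncentrality = 13 × 19.5 / 7² = 253.5/49 = 5.17, with 2 and 36 df.
- The critical F at 0.15 is 2.00. The noncentral F gives power **69.8%**.

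The stated figure reproduces, but it depends on this pattern of means. The same F test gives 56.9% for 0/4.5/4.5, 66.9% for 0/3/6 and 77.2% for 0/6/6.

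**Step 2: the planned comparison, one dose against placebo.**
- Standard error = 7 × √(2/13) = 2.746.
- Noncentrality = 4.5/2.746 = 1.64, or 6/2.746 = 2.19.
- The two-sided 0.15 critical t is 1.487 with 24 df (two groups only), or 1.471 with 36 df (error pooled over three groups).

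| True difference | t, 24 df | t, 36 df | Normal approximation |
|---|---|---|---|
| 4.5 | 56.6% | 57.1% | 57.9% |
| 5.25 | 66.7% | 67.2% | 68.2% |
| 6 | 75.8% | 76.3% | 77.2% |

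Pairwise power reaches 70% at 5.51 points (24 df) or 5.47 (36 df). For 70% at 4.5 points, 20 per arm would be needed by the t calculation, or 19 by the normal approximation.

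**Step 3: size as randomized.** 46/3 is about 15 per arm. Standard error = 7 × √(2/15) = 2.556. Power is 61.4% to 61.8% at 4.5 points and 80.6% to 81.0% at 6 (28 or 42 df). The 40 completers average 40/3 = 13.3 per arm. Because the primary analysis does not impute missing values, the 13-per-arm figures remain relevant.

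**Step 4: other tests that might lie behind the figure.**
- Pairwise, one-sided 0.15: 72.0% to 72.7% at 4.5 points and about 87% at 6. The SAP rules this out by stating two-sided.
- Both doses pooled (26) against placebo (13), two-sided: 67% at 4.5 points and 85% at 6.

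**Step 5: covariate adjustment.** With 13 per arm, reaching 70% at 4.5 points needs a residual SD of about 5.7. The covariate would have to explain 1 − (5.7/7)² = 34% of the variance. The documents give no figure for what the lung-function category explains.

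**The case against.** The strongest reply is that the text names its test. It claims 70% for an ANOVA, and that ANOVA has 69.8%. One power value cannot hold over a range of differences, so 4.5 and 6 are best read as the two doses' assumed effects. The Cohort 2 statement, which pairs a range of differences with a range of powers, supports this reading. The word *each* is in the synopsis alone. This much stands: a reader might infer an arithmetic error, and there is none. Nor does 70% belong to the omnibus test alone, since pairwise power reaches it at about 5.5 points, inside the stated range. The reply does not remove the mismatch, because the synopsis does say each group versus placebo and the planned analysis is pairwise.

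A second reply is that the SAP sets an alpha for success without saying whether one dose or both must meet it. Under effects of 4.5 and 6, the chance that at least one dose reaches two-sided 0.15 in its favour is about 83%, and that both do about 50% (simulation, 13 per arm, pooled error). That is fair, and it shows that 57% is not the power of the whole cohort. It is still the power of one named comparison at the lower difference.

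A reader might also infer that 60 mg was dropped because of its p-value of 0.21, read against an inflated power. The documents do not support this. The synopsis and protocol 7.3.2 give as reasons the greater improvement at 120 mg, the variability observed in a small sample and the absence of dose-limiting safety concerns. Neither cites non-significance or the 70%. Protocol 7.3.2 also reports standard errors, which show the precision obtained better than planned power does.

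**Conclusion.** The point holds as a mismatch between the stated power and the planned test. The 70% is correct for a three-group F test with means 0/4.5/6. It is not the power of each dose-versus-placebo comparison across 4.5 to 6 points, which runs from about 57% to 76% with 13 per arm and from about 61% to 81% with 15. The shortfall is confined to differences below about 5.5 points with 13 per arm.

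This rests on SD 7, two-sided 0.15 as in the SAP, equal arms and no gain from the covariate. A useful covariate would narrow the shortfall by an amount the documents do not allow us to estimate. The consequence is limited to accurate reporting and interpretation of a completed cohort. The choice of the Cohort 2 regimen and the separate Cohort 2 power statement are not called into question by it.

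**What to change.** In the protocol synopsis, protocol 13.2, SAP 6.1 and the study report, keep 70% as the historical basis for choosing 39 subjects and label it as the power of the three-group F test with means 0/4.5/6 (SD 7, alpha 0.15). In the synopsis, detach it from *each* comparison. Then add:

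> Each dose-versus-placebo comparison at two-sided 0.15 has about 57% power for 4.5 points and 76% for 6 points (13 per arm, SD 7, before covariate adjustment).

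The study report may also give the figures for about 15 per arm (61% and 81%). The cost is one or two sentences in each place, and a less favourable figure at the lower end of the range. No design, analysis or study procedure changes.

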**STUDY TREATMENT(S):**

**Test Product, Dose and Mode of Administration:** SPX-101 is a clear, sterile solution for inhalation consisting of 60 mg/mL SPX-101 drug substance in 0.9% sodium chloride adjusted to pH 7, intended for delivery as a nebulized aerosol by the investigational PARI eFlow nebulizer with PARI eTrack.

**Reference Therapy, Dose and Mode of Administration:**

The placebo for this study is sterile 0.9% saline adjusted to pH 7, free of preservatives and other excipients, suitable for inhalation via a nebulized aerosol by the investigational PARI eFlow nebulizer with PARI eTrack.

All drug product manufacturing and labeling will be managed by Spyryx Biosciences, Inc., and shipment and management of the investigational product will be the responsibility of PRA.

**DURATION OF TREATMENT:** 28 days

**STUDY EVALUATIONS:**

**Efficacy Variables:**

Primary Efficacy Variable:

- Change from baseline in ppFEV1 at Week 4

Secondary Efficacy Variables:

- Change from baseline in ppFEV1 at other study weeks
- Change from baseline in FEV1
- Change from baseline in forced vital capacity (FVC) and percent predicted FVC (ppFVC)
- Change from baseline in Cystic Fibrosis Questionnaire-Revised (CFQ-R)

**Safety Variables:**

- Incidence of treatment-emergent AEs (TEAEs)
- Changes in vital signs
- Changes in clinical laboratory tests, including urine and blood electrolytes
- Changes in electrocardiograms

**Pharmacokinetic Variable (for Cohort 1 Only):**

- Systemic exposure to SPX-101 (subset of subjects)

**Exploratory Variables**

- Incidence of pulmonary exacerbation, as defined by Fuchs [4] (See Appendix 3, [Section 18.3](#) for details)

**STATISTICAL METHODS:**

**Efficacy Analysis**

The primary endpoint is the change from baseline in ppFEV1 at Week 4 (Day 29).

The change from baseline in ppFEV1 at Week 4 will be summarized and compared between each treatment group and placebo. The primary analysis will be based on an analysis of covariance (ANCOVA), incorporating the categorical stratification variable of baseline lung function in Cohort 1, and the stratification variable of concomitant hypertonic saline use in Cohort 2.

Similar analysis will be performed for the change from baseline in ppFEV1 (Weeks 1 and 2), FEV1, ppFVC, and FVC at each visit (Week 1, 2, and 4).

The change from baseline in ppFEV1 at each visit (week 1, 2, and 4) will also be considered based on a mixed effect model for repeated measure (MMRM).

The change from baseline in CFQ-R respiratory domain score and physical domain score at Week 4 will be summarized and compared between each treatment group and placebo.

The number and percentage of subjects with pulmonary exacerbation will be summarized.

The effect of regular use of concomitant hypertonic saline will be explored across the primary and secondary endpoints.

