#### **13.6.4 Efficacy**

##### **13.6.4.1 Primary Efficacy Analysis**

The primary endpoint is the change from baseline in ppFEV1 at Week 4 (Day 29). The change from baseline in ppFEV1 at each visit (Weeks 1, 2, and 4) will be summarized and compared between each treatment group and placebo.

The primary analysis for the change from baseline in ppFEV1 at Week 4 will be based on an analysis of covariance (ANCOVA). For Cohort 1, the model will also include the stratification variable baseline lung function categories (ppFEV1 40.0% to 55.0% or 55.1% to 80.0%). For Cohort 2, the model will include the stratification variable of concomitant use of hypertonic saline.

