### 7.6 Predetermined Covariates and Prognostic Factors

In Cohort 1, baseline lung function ppFEV1 categories (percent predicted forced expiratory volume in 1 second between 40.0% and 55.0% vs between 55.1% and 80.0%) will be included as a covariate in the model of the analysis of covariance (ANCOVA).

In Cohort 2, the use (yes/no) of concomitant hypertonic saline and baseline ppFEV1 will be covariates in the ANCOVA model.

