#### Mixed Model for Repeated Measures

The change from baseline in ppFEV1 at each visit (week 1, 2, and 4) will also be evaluated using a mixed effect model for repeated measure (MMRM).

For Cohort 1, to evaluate treatment differences of ppFEV1 change from baseline across time points (week 1, 2 and 4), a likelihood-based mixed effect model repeated measures (MMRM) analysis will be run on ITT analysis set. The model will include the change from baseline in ppFEV1 as the dependent variable; the treatment, visit and treatment by visit interaction term will be treated as fixed effects, and covariates of baseline lung function category (ppFEV1 40.0% to 55.0% or 55.1% to 80.0% for Cohort 1). Subject will be treated as a random effect.

For Cohort 2, the MMRM analysis will be performed for the change from baseline in ppFEV1 to estimate the treatment difference at Week 4. The model will include all participants in the ITT population, and the dependent variable will be the observed change from baseline in ppFEV1 at each post-randomization visit. Covariates in the model will include the fixed categorical effects of treatment, concomitant use of hypertonic saline, visit and treatment by visit interaction, as well as the continuous fixed covariates of baseline ppFEV1 and baseline ppFEV1 by visit interaction.

Sponsor: SPYRYX Biosciences

Protocol no: SPX-101-CF-201

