## 13.0 Pooled Analyses Across Cohorts

The analyses specified in Sections 12 will be performed separately for each cohort, where applicable. In addition, the following summaries and analyses may be performed on the pooled cohorts for exploratory purposes. If performed, summaries and analyses will be presented by dose level (60 mg SPX-101 Cohort 1, 120 mg SPX-101 Cohort 1 and 2, and pooled placebo) and overall.

- Summary of subject disposition
- Summary of subject demographics
- Summary of CF history
- An ANCOVA as described in Section 12.6.1, using baseline ppFEV1 use as a covariate.

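### Cohort 1's models adjust for baseline ppFEV1 only as two bins; a labelled sensitivity analysis with continuous baseline would remove chance within-bin imbalance and match the Cohort 2 models

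*Protocol*

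**What the plan says.** **Cohort 1.** The protocol synopsis describes the primary ANCOVA as "incorporating the categorical stratification variable of baseline lung function in Cohort 1", and protocol 13.6.4.1 states: "For Cohort 1, the model will also include the stratification variable baseline lung function categories". SAP 7.6 and 12.6.1 repeat this, and the Cohort 1 MMRM lists only "covariates of baseline lung function category" next to treatment, visit and their interaction. No separate Cohort 1 model contains a continuous baseline term. If the normality or variance checks in SAP 12.6.1 fail, the fallback ANOVA or rank test drops even the category.

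**Cohort 2.** Protocol 13.6.4.1 names only hypertonic saline use as a covariate. SAP 12.6.1 goes further: "Also included in the ANCOVA model for Cohort 2 is baseline" ppFEV1. The Cohort 2 MMRM paragraph describes baseline ppFEV1 and its interaction with visit as continuous. That is the only place where the SAP states the form. For the ANCOVA, continuous is the natural reading because no categories are given.

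**Pooled.** SAP 13.0 lists, among analyses that may be run for exploratory purposes, "An ANCOVA as described in Section 12.6.1, using baseline" ppFEV1 as a covariate. The wording there is garbled and does not state the form.

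**Entry range.** Cohort 1 enrolled at 40.0-80.0% and Cohort 2 at 50.0-80.0% (protocol 9.4.1).

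**The concern.** Change in a lung function measure usually depends on its starting value, if only through regression to the mean. With two bins, a Cohort 1 subject at 56% and one at 79% are treated as having the same baseline. Stratified randomization balances the bins but not the values inside them, and with about 15 subjects per arm a chance difference of a few points is ordinary. Whatever part of that difference carries over into change stays in the dose-placebo estimate.

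The cohort with the widest baseline range has the coarsest adjustment, and the SAP gives no reason. SAP 6.2 explains why Cohort 2 was not stratified on ppFEV1, which is a different question. The final report will show 120 mg against placebo from both cohorts, possibly pooled, under different covariate sets.

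**Working it through.** **1. The reported Cohort 1 results (protocol 7.3.2).** Assume 40 Week 4 observations (the 40 completers) and 4 model parameters, giving 36 df.
- 60 mg: 3.08/2.411 = 1.28, two-sided p = 0.21 (reported 0.21).
- 120 mg: 5.19/2.606 = 1.99, two-sided p = 0.054 (reported 0.05).
- Gap between doses: 5.19 - 3.08 = 2.11 points.

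**2. Numbers per arm.** The TEAE percentages in protocol Table 1 imply 14 placebo, 15 at 60 mg and 16 at 120 mg (10/14 = 71.4%, 10/15 = 66.7%, 12/16 = 75.0%). Completers by arm are not given. The SE ratio 2.606/2.411 = 1.081 is close to that for 14/15/11 completers: sqrt(1/14 + 1/11)/sqrt(1/14 + 1/15) = 1.084. For 13/15/12 it is 1.056. So four or all five losses were probably in the 120 mg arm. This is an inference, not a documented fact.

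**3. What the bins leave.** Assume baseline is uniform on 40-80.
- Within-bin variance = 0.375 x 15²/12 + 0.625 x 25²/12 = 39.6, so SD 6.29.
- Total variance = 40²/12 = 133.3, so 39.6/133.3 = 30% remains.
- SD of the chance imbalance, 14 against 11 = 6.29 x sqrt(1/14 + 1/11) = 2.53 points.
- Effect on the 120 mg difference (1 SD): 0.13 x 2.53 = 0.33 to 0.3 x 2.53 = 0.76 points.

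**4. Simulation of the change in model.** Setup: 14/15/16 subjects, uniform baseline within bins, residual SD 6.4 (assumed), no true effect, five random losses from 120 mg, 6,000 trials per slope.

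| Slope (assumed) | SD of shift, bins to continuous | Shift exceeded in 10% of trials | Mean SE, bins | Mean SE, continuous |
|---|---|---|---|---|
| 0 | 0.43 | 0.7 | 2.57 | 2.61 |
| -0.13 | 0.56 | 0.9 | 2.59 | 2.60 |
| -0.2 | 0.67 | 1.1 | 2.62 | 2.60 |
| -0.3 | 0.88 | 1.4 | 2.68 | 2.60 |

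Both models are centred on zero throughout. Four losses instead of five give nearly the same shifts. The shift is not all removed imbalance: at slope 0 it is pure noise from estimating the slope (SD 0.43). Adding that to step 3 reproduces the table approximately: sqrt(0.33² + 0.43²) = 0.54 and sqrt(0.76² + 0.43²) = 0.87.

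**5. Baseline-related loss (hypothetical).** If the lowest-baseline subjects in each bin are the ones lost from 120 mg, the binned estimate is off by -0.3 to -0.6 points with four losses and -0.4 to -0.9 with five, over slopes -0.13 to -0.3. The continuous model stays near zero.

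**6. Planned power.** SAP 6.1 gives 70% with 39 subjects. The three-group F-test with means 0, 4.5 and 6, SD 7, 13 per arm and alpha 0.15 has noncentrality 13 x (3.5² + 1² + 2.5²)/49 = 5.17 and power 69.8%, so the figure reproduces. Adding continuous baseline with SD 7 x sqrt(1 - rho²) and one df fewer gives 69.8% at rho 0, 71.2% at 0.2 and 73.2% at 0.3. Here rho is the assumed within-stratum correlation of baseline with change.

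**The case against.** The strongest case against is that adjusting for the factor used in randomization is a sound, prespecified analysis, that its estimates are unbiased under random loss, and that a continuous baseline buys little precision. If the slope is near zero it costs some. All of that stands. Baseline spirometry is also tabulated by arm (SAP 12.2), change is explored by baseline stratum (SAP 12.6.4), and the pooled ANCOVA, if run, brings baseline ppFEV1 to the Cohort 1 arms. These help a reader see an imbalance, but none gives an adjusted Cohort 1 estimate comparable with Cohort 2's.

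A reader might infer more than the documents support, in three ways.

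- *That the 3.08 and 5.19 estimates feed the Cohort 2 sample size.* SAP 6.1 takes the effect and the SD of 7.58 from 120 mg and placebo subjects with baseline ppFEV1 of 50.0-80.0%, not from the full-cohort models.
- *That the dose choice is at risk or can still be changed by this.* Cohort 1 was locked, unblinded and analyzed before Cohort 2 (protocol 9.2 and 13.6.8). Its success level is two-sided 0.15: a downward shift of 0.9 points gives 4.29/2.606 = 1.65, p about 0.11, still inside. Only the tail of step 4 reaches the boundary: 3.79/2.606 = 1.45, p about 0.15, for a downward shift of 1.4.
- *That the binned estimate is biased in favour of 120 mg.* The bias in step 5 needs losses related to baseline, which the documents do not report, and that pattern would understate the drug.

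**Conclusion.** The point holds as a modest improvement to the analysis, not as a flaw that invalidates Cohort 1. Every separate Cohort 1 model uses two bins, while the SAP adds baseline ppFEV1 elsewhere. Under assumed slopes of -0.13 to -0.3 and a uniform baseline, the 120 mg estimate would move with an SD of about 0.5 to 0.9 points either way. That is 19% to 35% of its SE (0.5/2.606 and 0.9/2.606) and a noticeable fraction of the 2.11-point gap between doses. Precision is nearly unchanged, from about 1.5% worse to 3% better. An understatement of the drug by roughly 0.3 to 0.9 points is possible only under an unreported dropout pattern.

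The documents give neither the slope nor the baseline distribution nor completers by arm, so the sizes are conditional. The mismatch of covariates between cohorts does not depend on any of them.

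**What to change.** - Keep the Cohort 1 result under SAP Version 1.0 as the prespecified analysis and leave its model text as it is.
- In SAP 12.6.1 or 12.6.4, add a Cohort 1 sensitivity analysis, labelled as specified after unblinding: the ANCOVA with treatment, stratum and continuous baseline ppFEV1, and the MMRM with the same terms plus baseline-by-visit. Report it beside the prespecified estimates, and use it when Cohort 1 is compared with Cohort 2.
- In SAP 13.0, correct the wording and state that baseline ppFEV1 enters the pooled ANCOVA as a continuous covariate. State the same for the Cohort 2 ANCOVA in SAP 7.6 and 12.6.1.

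The cost is a few lines of SAP text, one rerun of existing programs, one degree of freedom in the ANCOVA (slightly more in the MMRM because of the interaction), and a post hoc label on the added Cohort 1 estimate.
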